CM4620-IE Dose and Route of Administration:	Patients randomized to receive Auxora (also known as CM4620 (zegocractin) Intravenous Emulsion) will receive one of three dose levels, 2.0 mg/kg (1.25 mL/kg), 1.0 mg/kg (0.625 mL/kg), and 0.5 mg/kg (0.3125 mL/kg), every 24 hours (±1 hour) for three consecutive days for a total of three infusions (Section 5.3). Auxora will be administered intravenously as a continuous infusion over 4 hours via a bag and tubing compatible with lipid emulsions and using a 1.2-micron filter.
Placebo Dose and Route of Administration	Placebo will consist of the emulsion without any active pharmaceutical ingredient CM4620. Patients randomized to receive Placebo will receive one of three dose volumes, 1.25 mL/kg, 0.625 mL/kg, and 0.3125 mL/kg, every 24 hours (±1 hour) for three consecutive days for a total of three infusions (Section 5.3). Placebo will be administered intravenously as a continuous infusion over 4 hours via a bag and tubing compatible with lipid emulsions and using a 1.2-micron filter.
Objectives:	 Primary: To assess the dose response and efficacy of three different dose levels of Auxora in patients with AP and accompanying SIRS; To assess the time to medically indicated discharge in patients who are responders to early tolerance of solid food intake versus non-responders. Secondary: To assess the safety and tolerability of varying doses of Auxora in patients with AP and accompanying SIRS.

Inclusion Criteria:

All of the following must be met for a patient to be randomized into the study:

- 1. The diagnosis of AP has been established by the presence of abdominal pain consistent with AP together with at least 1 of the following 2 criteria:
 - a. Serum lipase > 3 times the upper limit of normal (ULN);
 - b. Characteristic findings of AP on abdominal imaging;
- 2. The diagnosis of SIRS has been established by the presence of at least two of the following four criteria:
 - a. Temperature $< 36^{\circ}$ C or $> 38^{\circ}$ C;
 - b. Heart rate > 90 beats/minute;
 - c. Respiratory rate >20 breaths/minute or arterial carbon dioxide tension (PaCO₂) <32 mmHg;
 - d. White blood cell count (WBC) >12,000 mm³, or <4,000 mm³, or > 10% immature (band) forms;
- 3. At least one of the following criteria is also present:
 - a. A peripancreatic fluid collection or a pleural effusion on a contrastenhanced computed tomography (CECT) performed in the 24 hours before Consent or after Consent and before Randomization;
 - b. Abdominal examination documenting either abdominal guarding or rebound tenderness;
 - c. Hematocrit $\geq 44\%$ for men or $\geq 40\%$ for women;
- 4. The patient is > 18 years of age:
- 5. Lack of pancreatic necrosis, pancreatic calcifications, pancreatic pseudocysts and no evidence for previous necrosectomy or pancreatic surgery identified by CECT performed in the 24 hours before Consent or after Consent and before Randomization;
- 6. A female patient of childbearing potential who is sexually active with a male partner is willing to practice acceptable methods of birth control for 180 days after the last dose of study drug. A female patient must not attempt to become pregnant for 180 days;
- 7. A male patient who is sexually active with a female partner of childbearing potential is willing to practice acceptable methods of birth control for 180 days after the last dose of study drug. A male patient must not donate sperm for 180 days;
- 8. The patient is willing and able to, or has a legal authorized representative (LAR) who is willing and able to, provide informed consent to participate, and to cooperate with all aspects of the protocol.

Exclusion Criteria:

Patients with any of the following conditions or characteristics must be excluded from randomizing:

- 1. Expected survival <6 months;
- 2. Suspected presence of cholangitis in the judgment of the treating physician;
- 3. The patient has a known history of:
 - a. Organ or hematologic transplant;
 - b. HIV, hepatitis B, or hepatitis C infection;
 - c. Chronic pancreatitis (Appendix 7);
- 4. Current treatment with:
 - a. Chemotherapy;
 - b. Immunosuppressive medications or immunotherapy (Section 5.4 for list of prohibited immunosuppressive medications and immunotherapy);
 - c. Pancreatic enzyme replacement therapy;
 - d. Hemodialysis or Peritoneal Dialysis
- 5. The patient is known to be pregnant or is nursing;
- 6. The patient has participated in another study of an investigational drug or therapeutic medical device in the 30 days before randomization;
- 7. Allergy to eggs or known hypersensitivity to any components of study drug.

Study Design:

This double blind, randomized, placebo-controlled study will evaluate the efficacy, safety, and tolerability of three different dose levels of Auxora in patients with AP and accompanying SIRS.

Approximately 216 patients will be randomized 1:1:1:1 into one of 4 groups using a computer-generated randomization scheme accessed through an interactive voice/web response system (IXRS). Randomization will be first stratified by gender (male or female) and then by risk for organ failure in the gender subgroups (higher or lower). Higher risk for organ failure is defined by the presence of both an elevated hematocrit (HCT ≥44% for men or ≥40% for women) and hypoxemia (imputed PaO₂/FiO₂ ≤360). Lower risk for organ failure is defined by the absence of either or both an elevated hematocrit and hypoxemia (Figure 4). The PaO₂/FiO₂ will be determined using an arterial blood gas or imputed using pulse oximetry (Appendix 5).

All patients will have received a Screening CECT of the abdomen/pancreas before being randomized into the study. CECTs performed as standard of care (SOC) may be used as the Screening CECT but must have been performed in the 24 hours before Consent or after Consent and before Randomization (Section 8.12.12)

The Start of First Infusion of Study Drug (SFISD) should occur within 8 hours of the patient or LAR providing informed consent. Patients randomized to Group 1 will receive 2.0 mg/kg of Auxora intravenously every 24 hours $(\pm 1 \text{ hour})$ for a total of three doses. Patients randomized to Group 2 will receive 1.0 mg/kg of Auxora intravenously every 24 hours (±1 hour) for a total of three doses. Patients randomized to Group 3 will receive 0.5 mg/kg of Auxora intravenously every 24 hours (± 1 hour) for a total of three doses. Patients randomized to Group 4 will receive emulsion without any active pharmaceutical ingredient. Patients in Group 4 will receive one of three randomly assigned dose volumes, 1.25 mL/kg, 0.625 mL/kg, or 0.3125 mL/kg, which will be administered intravenously every 24 hours (± 1 hour) for a total of three doses. (Section 5.3) The dosing will be based on actual body weight obtained at the time of hospitalization or screening for the study. As described in the pharmacy manual, the upper limit of the volume of Auxora and volume of Placebo that will be administered will be 156.25 mL. The sponsor, investigators, pharmacists, and patients will be blinded to the assigned group. In the event of a medical emergency, investigators will be able to receive the treatment assignment if required to provide optimal care of the patient.

For all 4 groups, a study physician or appropriately trained delegate will perform study-specific assessments at screening, at the baseline assessment, immediately prior to the SFISD, and then every 24 hours until 240 hours after the SFISD, or until discharge if earlier. If patients remain hospitalized at Day 12, assessments will then be performed every 48 hours starting on Day 12 until Day 28, or until discharge if earlier. Patients discharged from the hospital before Day 25 will return at Day 30 (+5 days) to perform the Day 30 assessments. If patients are discharged on Days 25-29, the Day 30 assessments may be performed prior to discharge.

Patients will receive another CECT of the abdomen/pancreas at the Day 30 (± 5 days) visit. All CECTs performed as SOC after randomization and before the Day 30 CECT will also be captured. A blinded central reader will read the Screening, Day 30, and any SOC CECTs obtained between randomization and the Day 30 visit.

Patients will complete the modified American Neurogastroenterology and Motility Society Gastrointestinal Cardinal Symptom Index Daily Diary (mGCSI-DD) worksheet at the baseline assessment, at 96 hours, 168 hours, Day 14 and Day 21 (for patients who remain hospitalized on these days), on the day of discharge, and daily at bedtime after discharge until the Day 30 visit. Patients who are discharged on Days 25-29 will not complete the mGCSI worksheet after discharge.

It is recommended that all patients randomized in the study should receive care consistent with the 2018 American Gastroenterological Association (AGA) Institute Technical Review of the Initial Medical Management of Acute Pancreatitis. Patients should receive local SOC for the management of other medical conditions.

In patients with AP, the AGA strongly recommends early oral feeding (within 24 hours) rather than keeping the patient nil per mouth (Nil per Os, NPO). Patients randomized into the study, therefore, will be offered a low fat, \geq 500-calorie solid meal at each mealtime after the infusion of the first dose of study drug if alert and not on mechanical ventilation, or if not NPO for a planned surgery/medical procedure, or if not NPO because of an acute medical condition. If the patient does not wish to eat the solid meal when offered or is unable to tolerate the solid meal, they should then be offered a liquid meal. The same approach should occur at each subsequent mealtime until patient discharge. When patients eat a solid meal, it should be recorded if they ate \geq 50% of the meal and if they either vomited or experienced an increase in abdominal pain in the two hours after eating a meal.

It is also recommended that all patients randomized in the study should not be discharged from the hospital until solid food is tolerated, abdominal pain has resolved or been adequately controlled, and there is no clinical evidence of infection that would necessitate continued hospitalization. Tolerating solid food is defined as eating ≥50% of a low fat, ≥500-calorie solid meal without an increase in abdominal pain or vomiting. If the patient is not tolerating either solid or liquid meals, tube feedings should be considered.

All protocol required laboratory testing, except biomarker and pharmacokinetic (PK) samples, will be performed at the local laboratory. Results from the biomarkers and PK blood samples collected as part of the protocol and being tested at a central lab will not be available to assist the Principal Investigator (PI) or treating physician in managing the patient.

Efficacy Assessments:	Efficacy assessments will include the following: Enhanced Recovery Strategy for Tolerance of Solid Food Modified Gastrointestinal Cardinal Symptom Index Score CECT of the Pancreas Pain Numeric Rating Scale (PNRS) score Organ Failure scores Vital sign measurements Laboratory measurements Concomitant medications
Safety Assessments:	Safety assessments will include the following: • Vital signs measurements • Laboratory measurements • Concomitant medications • Treatment-emergent adverse events (TEAEs) and serious adverse events (SAEs)

Efficacy	Primary endpoint
Endpoints:	Time to solid food tolerance
	Secondary endpoints:
	• Solid food tolerance at 48 hours, 72 hours, and 96 hours after the SFISD
	and at discharge
	Time to medically indicated discharge
	Length of stay in the hospital
	• Length of stay in the intensive care unit (ICU) for patients admitted to the ICU
	Re-hospitalization for AP by Day 30
	• Change in severity of AP by CTSI score from screening to Day 30
	● Development of pancreatic necrosis ≥30% and >50%
	• The persistence of SIRS ≥48 hours after the SFISD
	• Incidence, severity, and duration of organ failure
	Mortality by Day 30 Change in pair seem and anisid year.
	Change in pain score and opioid use
	Exploratory endpoints:
	Development of infected pancreatic necrosis
	Development of sepsis
	Hospital procedures for the management of pancreatic necrosis
	Change in GCSI-DD score
	Change in albumin
	• Change in absolute neutrophil count (ANC)/absolute lymphocyte count
	(ALC) ratio and IL-6 levels
	Change in urine neutrophil gelatinase-associated lipocalin (NGAL)
Safety	The incidence of TEAEs and SAEs
Endpoints	The intensity and relationship of TEAEs and SAEs
	Clinically significant changes in vital signs and safety laboratory results
Pharmacokinetic	In patients at selected sites, sparse sampling of plasma will be employed for
Assessments:	PK assessment after finishing the first and third doses of study drug.
Statistical	Sample Size Calculations
Considerations	A sample size of 216 patients will be randomized into four groups on a
	1:1:1:1 basis, resulting in 54 patients randomized into each group. This
	sample size will provide 86% power for testing the difference in two
	populations having a median length of time of 72 and 144 hours, respectively,
	to tolerating solid food based on a log-rank test. This sample size will
	provide 80% power with a two-sided alpha of 0.05 (using the chi-squared
	test) to detect a 45% response rate for tolerating solid food in a Auxora

dose group versus a 20% response rate in the Placebo group in the 72 hours after completion of the first study drug infusion.

Treatment Populations

- Modified Intent to Treat Population will consist of all randomized patients who receive any amount of study drug
- The Per-Protocol Population (PP) will consist of all randomized patients who complete the study and have no major protocol violations
- The PK population will consist of all randomized patients who receive any amount of active study drug and who have at least one post baseline PK sample analyzed

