1.4 Pre-Clinical Development of Zegocractin

1.4.1 Pre-Clinical Safety and Toxicology Studies

Safety pharmacology studies conducted in rats indicated no zegocractin-induced adverse effects on central nervous or respiratory systems. Dose-limiting adverse clinical and cardiovascular effects were noted in a single telemetered cynomolgus monkey dosed at 25 mg/kg intravenously (IV) with Auxora (zegocractin intravenous emulsion). Cardiovascular data at lower doses (1, 3 and 10 mg/kg) showed transient, non-dose-related, slight-to-moderate increases in systolic/diastolic arterial blood pressures and negative chronotropic effects (mild and non-adverse) at all doses and in placebo treated animals.

Repeat-dose toxicity studies conducted in both rats and monkeys showed no observable adverse effect levels (NOAELs) of 25 mg/kg/day and 3 mg/kg/day, respectively. *In vitro* genetic toxicity studies were negative in the Ames bacterial reverse mutation assay and weakly positive/equivocal in a micronucleus assay conducted in human peripheral blood lymphocytes. A subsequent *in vivo* micronucleus study conducted in rats involving two different endpoints (bone marrow micronucleus and liver Comet assays) showed no evidence of DNA reactivity. Based on the results of the complete battery of genotoxicity testing, the weight of evidence indicates that zegocractin is neither mutagenic nor clastogenic. Hemolysis testing concluded that zegocractin placebo was

compatible with human plasma and non-hemolytic in human blood. Specific local tolerance studies to examine irritation/inflammation at the injection site were not performed, but no evidence of compound-related or vehicle-related local irritation was observed in the repeat-dose toxicity studies in rat and monkey. Finally, *in vitro* 3T3 results indicated that zegocractin is potentially phototoxic, so appropriate precautions are being taken in clinical trials.

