In the SAD study (CM4620-101), interim non-compartmental pharmacokinetic (PK) analysis indicates that Auxora likely distributes to three compartments. Plasma concentrations of compound rise steadily during the 4-hour infusion, with T_{max} achieved at the end of infusion (4 hours). After the end of infusion, there is a rapid and prominent distribution phase followed by a prolonged period of residual drug levels. The terminal elimination phase has not yet been fully characterized as it appears to be much longer than was anticipated based on pre-clinical PK data in mouse, rat, dog and monkey. Plasma concentrations during the terminal phase are approximately 5% of maximum serum concentration (C_{max}) values and, as indicated above, to date there have been no clinically significant AEs reported during this phase. Plasma exposures, defined by the area under the concentration-time curve (AUC)_{0-24h}, appear to be dose-proportional and reached a

maximum of 6710 ng*h/mL in Group 5, which is 4.3-fold below the mean AUC_{24h} in monkey at the NOAEL (29,000 ng*hr/mL).

In the MAD study (Table 2) of Auxora (CM4620-102), subjects in the first group were randomized to receive a single dose of active treatment, 0.50 mg/kg, versus placebo for seven consecutive days. Eight healthy subjects were enrolled in the first group, with five receiving active treatment and three receiving placebo. One of the subjects received placebo at the maximum dose volume of emulsion, 1.3 mL/kg, for 7 days, whereas all others were dosed on a weight-based adjustment of dose volume. There were no SAEs and no AEs classified as moderate or severe in intensity. There were 15 clinical AEs that were all classified as mild. In each case, no action was taken with respect to study treatment because of the AEs. No laboratory abnormalities were observed that were considered clinically significant.

Table 2. MAD (CM4620-102)

Group	Active Treatment Daily for 7 days	Number of Active Treatment Subjects	Number of Placebo Treatment Subjects	IV Dose Volume (mL/kg)
1	0.5 mg/kg	5	3	0.3125a
2	1.0 mg/kg	6	2	0.625

IV = intravenous

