At 72 hours or Discharge (if earlier), 7 of 14 (50%) of patients receiving Auxora+SC (all doses) were able to tolerate solid food, defined as eating \geq 50% of a solid meal without vomiting or an increase in pain, compared to 1 of 7 (14%) patients receiving SC alone. At Day 10 (216 hours or Discharge), 13 of 14 (92.9%) patients receiving Auxora+SC (all doses) were able to tolerate solid food compared to 3 of 7 (43%) patients receiving SC alone. The median (min, max) time to tolerating solid food for patients receiving the low dose regimen+SC was 57 hours (17, 121), for patients receiving the high dose regimen, 78.5 hours (39, 440) and for patients receiving only SC, 100 hours (22, 720).

Five of 14 patients (35.7%) randomized to Auxora+SC (all doses) had persistent SIRS, defined as SIRS lasting continuously for \geq 48 hours starting on or after the Day 1 (0 hour) assessment, compared to 5 of 7 patients (71.4%) in the SC alone group.

A blinded central reader read all Screening, Day 5 or Discharge, and Unscheduled contrast-enhanced computed tomography (CECT) scans and gave a score for the severity of AP using the CTSI scoring system. One patient treated with the high dose regimen+SC did not receive a CTSI score at either the Screening or Day 5 or Discharge CECTs. One patient treated with SC alone did not receive a CTSI score at Screening because contrast was not given. On the Screening CECT, 8 patients treated with Auxora-IE+SC (all doses) had moderate or severe AP based on the CTSI score. Three of the 8 (37.5%) patients with moderate or severe AP improved with treatment to have mild AP based on the CTSI score on the Day 5 or Discharge CECT. On the Screening CECT, 4 patients treated with SC alone had moderate or severe AP. None of the 4 (0%) patients improved to have mild AP by the Day 5 or Discharge CECT.

The median length of stay (min, max) for patients randomized to Auxora-IE+SC (all doses) and SC alone were 3.70 (1.5, 18.3) and 6.02 (1.1, 30.0) days, respectively.

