8 VISITS AND ASSESSMENTS

8.1 Screening

The PI or designee must provide informed consent to the patient, or LAR, allowing the patient or LAR adequate time to consider, ask questions and receive answers, prior to agreeing to participate.

• Record the time of the patient or LAR provides informed consent

After informed consent is obtained, the following procedures are to be performed unless already performed as part of SOC:

- Record the time of the onset of abdominal pain that sent patient to ER
- Record demographics and medical history
- Record list of medications being taken prior to hospitalization
- Record vital signs closest to the time of informed consent
- Perform an abdominal examination specifically assessing for guarding and rebound tenderness (see Section 8.12.3)
- Draw serum pregnancy test if the patient is a female of childbearing potential analyze at local lab
 - If already performed as part of SOC, record results. Testing may be performed on blood drawn in the previous 12 hours prior to Consent or following consent but prior to randomization.
- Draw a blood sample for serum lipase–analyze at local lab
 - If already performed at local lab as part of SOC, record results. Testing may be performed on blood drawn in the previous 12 hours prior to Consent or following consent but prior to randomization.
- Draw a blood sample for CBC, differential, and platelets—analyze at local lab
 - If already performed at local lab as part of SOC, record results. Testing may be performed on blood drawn in the previous 12 hours prior to Consent or following consent but prior to randomization.
- Determine if SIRS is present (see Section 8.12.13)
- Obtain CECT of the abdomen/pancreas and determine if there is evidence of pleural
 effusion, peripancreatic fluid collection, pancreatic necrosis, pancreatic calcifications,
 pancreatic pseudocysts, and previous necrosectomy/previous pancreatic surgery are
 present on a CECT
 - o If CECT already performed in the 24 hours prior to the patient or LAR providing informed consent, use results from that CECT (see Section 8.12.12)

If the patient satisfies all of the inclusion criteria and none of the exclusion criteria, immediately proceed to Baseline Assessment.

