8.12.13 Systemic Inflammatory Response Syndrome (SIRS)

The physician, or appropriately trained designee will determine the presence of SIRS at Screening. The most extreme value for each criterion in the 24 hours before consent may be used. SIRS is defined as the presence of at least 2 of the 4 criteria:

- Temperature $< 36^{\circ}$ C or $> 38^{\circ}$ C
- Heart rate > 90 beats/minute
- Respiratory rate > 20 breaths/minute or arterial carbon dioxide tension (PaCO2)
 32 mmHg
- White blood cell count (WBC) >12,000 mm3, or < 4,000 mm3, or > 10% immature (band) forms

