8.7.7 Persistence of SIRS ≥48 Hours After the SFISD

The persistence of SIRS ≥48 Hours after the SFISD is defined by the presence of at least two of the following four criteria at the first visit 48 hours after the SFISD:

- Temperature $< 36^{\circ}$ C or $> 38^{\circ}$ C;
- Heart rate > 90 beats/minute;
- Respiratory rate >20 breaths/minute or arterial carbon dioxide tension (PaCO2) <32 mmHg;

Protocol CM4620-203 CONFIDENTIAL Page 21 of 31

• White blood cell count (WBC) >12,000 mm3, or <4,000 mm3;

The proportion and 95% CI of patients who developed persistence of SIRS ≥48 Hours After the SFISD will be displayed and analyzed in the same way as the re-hospitalization for acute pancreatitis through Day 30. If the patient is discharged before 48 Hours after the SFISD, the last available post-treatment data will be used to define the SIRS status at 48 hours after the SFISD based on the LOCF method.

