8.10.2 Vital Signs

Vital signs will include temperature, systolic and diastolic blood pressure, respiratory rate (breaths per minute), heart rate (beats per minute) and QTc (milliseconds). Vital signs will be examined at each scheduled visit and time point. Clinically significant, treatment-emergent findings will be reported as AEs. In addition, vital signs results will be flagged as potentially clinically significant (PCS) if they meet the criteria which are defined below:

- Pulse rate >130 bpm
- Pulse rate <45 bpm
- Diastolic blood pressure >100 mmHg
- Systolic blood pressure >155 mmHg
- Systolic blood pressure <80 mmHg
- Respiration rate >25 breaths/min
- Body temperature ≥39 °C
- OTc >500 milliseconds

The number and percent of patients meeting each PCS criterion at each scheduled visit and time point will be summarized by the actual treatment and then by the overall treatment.

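### No vital signs are scheduled at the start of the first infusion or at the end of any infusion, so the planned safety tables could miss a brief, silent change near peak drug level; a cheap addition would close the gap

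*Protocol*

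**What the plan says.** Timing of vital signs:

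- Protocol synopsis, Study Design: assessments take place "at screening, at the baseline assessment, immediately prior to the SFISD, and then every 24 hours until 240 hours after the SFISD". The sentence does not say which measurements are made at each time.
- Protocol 8.1 (Screening): "Record vital signs closest to the time of informed consent". Under 8.4 the first infusion (SFISD) should begin within 8 hours of consent.
- Protocol 8.2 (Baseline Assessment) lists oxygenation, pain, symptoms, weight and laboratory samples, but no heart rate, blood pressure, temperature or respiratory rate.
- Protocol 8.4 lists concomitant medications, infusion times and a PK sample within 2 hours of the end of the first infusion. It lists no vital signs.
- Protocol 8.5 to 8.7 record vital signs at 24, 48 and 72 hours, the last only in patients still in hospital.
- The Vital Signs row of Appendix 8, repeated in SAP Table 1, agrees: marked at Screening, blank at Baseline, randomization and SFISD, marked again from 24 hours.

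Peak level: Protocol 1.5.1 reports that "Plasma concentrations of compound rise steadily during the 4-hour infusion", with the maximum reached when the infusion ends.

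Analysis: Protocol 2.4 makes clinically significant vital-sign changes a safety endpoint. SAP 8.10.2 says "Vital signs will be examined at each scheduled visit and time point" and counts threshold alerts there. SAP 8.1.4.1 takes as baseline the last value at or before the SFISD.

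**The concern.** The secondary objective is the safety and tolerability of three doses. If a dose moves pulse or blood pressure, the likeliest time to see it is around the end of infusion, and no reading is tied to that time. Under Protocol 9.1 an abnormal reading becomes an adverse event only if it causes signs or symptoms, needs active intervention, or leads to interruption or discontinuation of study drug. A short-lived change that does none of these would enter neither the adverse-event tables nor the vital-sign tables, and the alert table could be read as showing no effect when the relevant hours were not sampled.

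The baseline is a second, smaller issue. With no reading at the SFISD, the SAP rule falls back to the set taken near consent, in patients whose condition may change over those hours.

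**Working it through.** The documents give no figure for this point, so the check is clock arithmetic from the SFISD (0 h).

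**Inputs.** Infusion length 4 h (Protocol 7.5). Infusions 2 and 3 start at 24 and 48 h, each ±1 h (8.5, 8.6). Reading windows are ±1 h at 24 and 48 h and ±2 h at 72 h (Appendix 8).

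**Lag from end of infusion to the next scheduled reading.** Shortest lag = (reading − its window) − (end + start window). Longest lag = (reading + its window) − (end − start window).

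| Infusion | Nominal end | Next reading | Nominal lag | Range |
|---|---|---|---|---|
| 1 | 4 h | 24 h | 20 h | 23 − 4 = 19 to 25 − 4 = 21 h |
| 2 | 28 h | 48 h | 20 h | 47 − 29 = 18 to 49 − 27 = 22 h |
| 3 | 52 h | 72 h | 20 h | 70 − 53 = 17 to 74 − 51 = 23 h |

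A patient discharged between 52 and 72 h has no further scheduled set until Day 30.

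**Consent to first post-dose reading.** Nominally 0 + 24 = 24 h to 8 + 24 = 32 h.

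**Chance readings near an infusion.**
- Within the ordinary windows: infusion 2 may start at 23 h and the 24-hour reading may be taken as late as 25 h, which is 2 h into that infusion. Section 8.5 requires the laboratory, PK and urine samples before the second dose, but not the vital signs. The same holds at 48 h.
- With an infusion brought forward under 5.3: infusion 2 starting 6 h early, at 17 to 18 h, ends at 21 to 22 h. The 24-hour reading (23 to 25 h) then falls 1 to 4 h after its end.

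**Level after the first infusion, Day 1 only.** Day 1 values come from dividing the Day 7 figures in Protocol 1.5.1 by the stated accumulation ratios, assuming a linear rise from zero during infusion.
- 1.0 mg/kg: AUC 6830/2.6 = 2627 ng·h/mL; Cmax 637/1.4 = 455 ng/mL. Infusion part 0.5 × 455 × 4 = 910. Mean over the next 20 h = (2627 − 910)/20 = 86 ng/mL, about 19% of Cmax.
- 0.5 mg/kg: AUC 3190/2.6 = 1227; Cmax 363/1.6 = 227. Infusion part 0.5 × 227 × 4 = 454. Mean = (1227 − 454)/20 = 39 ng/mL, about 17% of Cmax.

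These percentages do not carry over to later doses, because AUC accumulates more than Cmax. On Day 7 at 1.0 mg/kg, assume a pre-dose level between 0 and 6830/24 = 285 ng/mL:
- Pre-dose 0: (6830 − 0.5 × 637 × 4)/20 = 278 ng/mL, about 44% of 637.
- Pre-dose 285: (6830 − 0.5 × (285 + 637) × 4)/20 = 249 ng/mL, about 39% of 637.

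The 48- and 72-hour readings would lie between the Day 1 and Day 7 pictures.

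**The case against.** The case for leaving the schedule alone is substantial.

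- **Animal data.** At 1, 3 and 10 mg/kg the monkey data "showed transient, non-dose-related, slight-to-moderate increases in systolic/diastolic arterial blood pressures and negative chronotropic effects". Protocol 1.4.1 calls the chronotropic effects mild and non-adverse, and the changes also occurred on placebo. A reader might infer a drug-specific dose effect; a change unrelated to dose and shared with vehicle does not show one.
- **Human data.** Phase 1 used continuous ECG recording and reported no sustained blood-pressure rise and no heart-rate effect (single dose) or no sustained one (repeat dosing). Phase 2a reported no untoward vital-sign changes at doses up to 2.08 mg/kg. This lowers the concern. It does not settle it: the word sustained leaves brief changes open, and the Phase 2a summary does not say when readings were taken.
- **Safety net.** Appendix 8 schedules an adverse-event evaluation at the SFISD, and Protocol 9.3 requires chart review. A reader might infer that peak effects cannot be seen at all. That goes too far: the gap is in systematic, analysed data, not in bedside observation.

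The objection reduces the importance of the point. It does not alter the schedule: no reading is planned at the SFISD or at the end of an infusion.

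**Conclusion.** The point stands as a cheap improvement to a safety endpoint. No vital-sign set is planned between the consent-time reading and 24 hours, and none is tied to the end of any of the three infusions; the nominal lag is 20 hours each time. This assumes that sites follow the nominal times, that only scheduled eCRF visits enter the tables (SAP 8.1.6 and 8.10.2), and that the peak in patients comes at the end of infusion as in healthy subjects. Whether any effect is being missed, and how large it might be, cannot be told from the documents.

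Three stronger readings are tempting and are not supported:

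- **That no on-treatment reading can fall near an infusion, or that only an early infusion could change this.** The ±1 h windows alone allow it. Such readings are incidental.
- **That the synopsis contradicts Sections 8.2 and 8.4.** The synopsis sentence names no measurements, and 8.4 does list a pre-infusion procedure (concomitant medications).
- **That the SIRS persistence endpoint must be redefined.** Entry SIRS is indeed lenient ("The most extreme value for each criterion in the 24 hours before consent may be used"), and SAP 8.7.7 looks once, "at the first visit 48 hours after the SFISD". But Phase 2a counted continuous SIRS "starting on or after the Day 1 (0 hour) assessment", so it too admitted SIRS beginning after dosing; it differed in requiring continuity. The share of patients without SIRS at dosing is not given, so any dilution is unquantified. A time-0 status built on the screening blood count could use a sample drawn 12 h (8.1) to 24 h (8.12.7) before consent, hence up to 12 + 8 = 20 to 24 + 8 = 32 h old at dosing.

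**What to change.** 1. In Protocol 8.4 to 8.6, Appendix 8 and SAP Table 1, add heart rate, blood pressure, temperature and respiratory rate, copied from the routine chart immediately before the SFISD and at the end of each infusion, within +2 h as already allowed for the first PK sample.
2. State in the SAP that the pre-SFISD set is the vital-sign baseline.
3. In SAP 8.10.2, add an end-of-infusion alert table using the existing thresholds, and the change from the pre-SFISD value at the end of each infusion, both by dose group.
4. Leave SAP 8.7.7 as it is.

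Cost: 1 + 3 = 4 more chart-derived entries per patient who receives all three infusions, a schedule amendment and a few lines of SAP text. No added visit is needed. If the amendment comes after some patients have been treated, the values may be recoverable from their charts; otherwise the report should state that the vital-sign tables do not describe the end of infusion.
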